1.4 Rationale

The IMpower133 clinical trial evaluated chemotherapy and atezolizumab for first line treatment of patients with untreated ES SCLC. The results from the trial led to an FDA approval and established this regimen as a new standard of care. However, while patients with brain metastases were allowed, prior cranial radiation was required for these patients. Furthermore, only 9% of enrolled patients had brain metastases. There remains an urgent need to define clinical outcomes for patients treated with chemotherapy and atezolizumab with asymptomatic, untreated brain metastases.

Recent studies with systemic immunotherapy in brain metastases patients have demonstrated that outcomes for patients with and without brain metastases are generally similar. The IMpower133 study demonstrated PFS outcomes of 5.2 months for the atezolizumab arm versus 4.3 months for the placebo arm. Thus, we hypothesize that atezolizumab plus chemotherapy (i.e. carboplatin and etoposide) will improve intracranial progression free survival (iPFS) in patients with brain metastases from SCLC relative to historical controls (\geq 5.2 months vs. 4 months).

This study will enroll patients with asymptomatic brain metastases and untreated ES SCLC. Patients will be treated with combination carboplatin, etoposide, and atezolizumab. Restaging radiographic imaging will occur every 6 weeks (approximately every 2 cycles of treatment). At time of progression, patients can pursue standard of care treatment and radiation therapy off study. Our hypothesis is that the addition of atezolizumab will improve intracranial progression free survival in patients with untreated brain metastases. Furthermore, the study will provide valuable insight in the clinical outcomes of the patient population with ES SCLC and brain metastases. In general, chemotherapy response rates are expected to be high, and immune checkpoint therapy is known to have efficacy in other CNS malignancies. We believe treatment with systemic therapy alone will 1) delay time to WBRT 2) preserve quality of life longer 3) allow a subpopulation of patients to avoid WBRT and 4) be able to avoid a detrimental impact on survival given the close radiographic follow up.

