2.2 Endpoints

2.2.1 Primary Endpoint

- Intracranial PFS is defined as the time from Day 1 of treatment until the criteria for intracranial disease progression is met as defined by RANO-BM or death as a result of any cause, whichever comes first.

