6.4 Protocol Therapy Discontinuation

In addition to discontinuation from therapy related to toxicities as outlined above, a subject will also be discontinued from protocol therapy and followed per protocol under the following circumstances outlined below. The reason for discontinuation of protocol therapy will be documented on the electronic case report form (eCRF)

- Documented disease progression based on RECIST 1.1
- Site investigator determines a change of therapy would be in the best interest of the subject
- Subject requests to discontinue protocol therapy, whether due to unacceptable toxicity or for other reasons
 - In a subject decides to prematurely discontinue protocol therapy (“refuses treatment”), the subject should be asked if he or she may still be contacted for further scheduled study assessments. The outcome of that discussion should be documented in both the medical records and in the eCRF.
- Female subject becomes pregnant
- Protocol therapy is interrupted for ≥ 63 days.

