7. STUDY CALENDAR & EVALUATIONS

Study Evaluation Cycle = 21 days	Screening	On Treatment Cycles 1-4			Maintenance Cycles 5+	Safety follow up visit	Long-term Follow up
	-28 days	Day 1 ± 2 days	Day 2	Day 3	Day 1 ± 2 days	30 days post last dose + 7 days	Every 3 months (±14 days)
REQUIRED ASSESSMENTS							
Informed Consent	X						
Medical History	X						
Physical Exam	X	X			X	X	
Vital signs and ECOG Performance Status	X	X			X	X	
Quality of Life Questionnaires		x ³			x ³	x ³	
AEs & concomitant medications	X	X			X	X	
LABORATORY ASSESSMENTS							
Complete Blood Cell Count with diff (CBC)	X	x ⁹			X	X	
Comprehensive Metabolic Profile (CMP)	X	x ⁹			X	X	
PT/INR and aPTT	X						
Thyroid Function Testing	X	C3D1			x ⁴	X	
Hepatitis Testing	X						
Pregnancy test (serum or urine) (WOCBP)	X	x ⁴			x ⁴		
DISEASE ASSESSMENT							
CT of chest	x ⁵	C3D1			x ⁵		x ⁵
CT or MRI of abdomen and pelvis	x ⁵	C3D1			x ⁵		x ⁵
MRI Brain	x ⁵	C3D1			x ⁵		x ⁵
TREATMENT EXPOSURE							
Atezolizumab		D1			x ⁶		
Carboplatin		D1					
Etoposide		D1-D3					
SPECIMEN COLLECTION							
Archival Tumor Tissue	x ⁷						
Blood Samples		x ⁸				x ⁸	
FOLLOW-UP							
Survival Status, Subsequent Therapy							X

- 1: Medical History; other data to be obtained during this assessment includes a smoking history questionnaire and trial awareness question. In addition, prior anti-cancer treatment should be documented including medications (chemotherapy, checkpoint inhibitors, etc) radiation or surgery. In addition, diagnosis and staging to include pathology report and TNM staging documentation. Histological confirmation per VALG of Stage IV Stage Small Cell Lung Cancer (SCLC)- extensive stage. Prior genomic testing (ie NGS) and PD-L1 results are required if available.
- 2: Physical exam to include a complete neurological exam. Vital signs to include temperature, pulse, respirations, blood pressure weight, and height (screening only) and ECOG performance status.
- 3: Quality of life evaluations include FACT-Br, FACIT-Fatigue, and Godin Leisure-Time Exercise Questionnaire. Questionnaires to be completed Cycle 1 Day 1 then every other Cycle of treatment (6 weeks; \pm 1 week) and at the D30 Safety Visit.

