- 4: CBC with platelet and differential (white blood cell count, absolute neutrophil count, hemoglobin and platelet count). Serum chemistries (creatinine, glucose, total bilirubin, aspartate transaminase [AST] and alanine transaminase [ALT] and calcium). Thyroid Function testing should be performed at screening then every 6 weeks (i.e. every other cycle). TSH will be obtained. T4 and T3 including free versus total testing is at the discretion of the site investigator. Hepatitis testing to be performed at screening if results as described in the inclusion criteria are not known. For women of childbearing potential (WOCBP): urine or serum β hCG if clinically appropriate. If a urine test is done and it is positive or cannot be confirmed as negative, a serum pregnancy test will be required. Testing is required within 24 hours prior to initiation of study treatment. During treatment, testing should be performed every 3 weeks (on Day 1 of each cycle prior to administering treatment).
- 5: Tumor response assessment will consist of evaluation by MRI scan of the brain and CT scans of chest +/- abdomen and pelvis. If unable to perform MRI due to medical reasons, CT with contrast is acceptable. Brain MRI used to diagnose brain metastases allowed or a CT with contrast is acceptable. The abdomen/pelvis may be scanned at follow-up timepoints only if positive disease was detected at baseline. Radiology imaging to be performed at screening (within 6 weeks prior to C1D1), then every 6 weeks (prior to Cycle 3 Day 1 and Cycle 6 Day 1) then every 9 weeks (prior to Cycle 9 and so on). Imaging needs to occur every time point regardless of any delay in treatment. Tumor imaging to be done in the follow up period is at discretion of site investigator. If tumor assessments are available for subjects who have not yet experienced progressive disease (PD) at the time treatment is discontinued, the follow-up tumor evaluations will be documented in the eCRF until PD or death is confirmed, or until another treatment is initiated.
- 6: Induction treatment will consist of 4 cycles of Atezolizumab (1200 mg on Day 1) combined with carboplatin (5-6 AUC on Day 1) and etoposide (80-100 mg/m² on Days 1-3). After 4 cycles of induction treatment, subjects will receive atezolizumab maintenance 1200 mg on Day 1 of each 3-week cycle. Subjects will receive treatment until disease progression, unacceptable drug-related toxicity, or withdrawal from study for any reason.

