- 7: Archival tissue is required if available. Archival tissue should be identified and requested at screening and shipped by Cycle 2 Day 1, if available. If archival tissue is not available, the subject may still be eligible for the trial. See CLM for collection, labeling, and shipping instructions. Subjects will also be consented for optional storage of any remaining tissue samples after protocol-specified studies are complete. These samples will be stored for future unspecified cancer-related research and are considered “banking samples”.

8: Blood (whole blood for PBMCs, plasma and buffy coat for germline DNA) for correlative analysis will be drawn prior to treatment on Cycle 1 Day1, Cycle 3 Day 1 and at the D30 safety visit/progression. Additional details regarding correlatives can be found in Section 8 and the CLM.

9: If screening (baseline) CBC and Chemistry (CMP) were performed within 7 days of Day 1 of treatment, these do not need to be repeated. All laboratory assessments should be done prior to treatment.

10: Safety Follow Up: The safety follow-up visit should only occur when subjects permanently stop study treatment for whatever reasons (toxicity, progression, or other reason) and should be performed 30 days (+ 7 days) after the last dose of treatment. Subjects who have an ongoing Grade ≥ 2 or serious AE (SAE) at this visit will continue to be monitored by a member of the study team until the event is resolved, stabilized, determined to be irreversible by the site investigator or a new anti-cancer treatment starts, whichever occurs earlier.

11: Long Term Follow Up: For subjects who discontinue for reasons other than progressive disease, radiographic disease assessment should be performed every 9 weeks until progression, initiating a new cancer treatment, withdrawing consent or becoming lost to follow-up. The scan interval may be reset if scans were done sooner for clinical reasons and the type of scan may be left to discretion of the site investigator. This imaging may be done locally. Once disease progression is documented, subjects will be followed for survival every 3 months for 1 year from documented progression. Follow up may be accomplished via clinic visit, phone call, or other avenues as appropriate. A window of ± 14 days will be applied to follow up.

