12.2.1 Definition of Primary Endpoint

The primary endpoint of the study is intracranial progression free survival (iPFS), which is defined as the time from Day 1 of protocol treatment until the criteria for iPFS is met as defined by RANO-BM or death from any cause, whichever comes first.

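### iPFS stays open until intracranial progression or death, but required brain imaging, as most naturally read, stops at progression in any site, and no iPFS censoring rule is stated

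*Combined protocol and SAP*

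**What the plan says.** **Endpoint.** Section 2.2.1 runs iPFS from Day 1 "until the criteria for intracranial disease progression is met as defined by RANO-BM or death as a result of any cause". Section 12.2.1 repeats this: "until the criteria for iPFS is met as defined by RANO-BM or death from any cause, whichever comes first". Section 9.2.2 makes CNS response independent of systemic response, so extracranial progression alone is not an iPFS event.

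**Treatment.** Section 6.4 stops protocol therapy at "Documented disease progression based on RECIST 1.1", without naming a compartment. Section 1.4 adds: "At time of progression, patients can pursue standard of care treatment and radiation therapy off study".

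**Imaging after treatment.**
- Section 7, footnote 11: "For subjects who discontinue for reasons other than progressive disease, radiographic disease assessment should be performed every 9 weeks until progression", or until new cancer treatment, withdrawal of consent or loss to follow-up. After documented progression it provides survival follow-up every 3 months for 1 year.
- Section 7, footnote 5: "Tumor imaging to be done in the follow up period is at discretion of site investigator". It provides for eCRF recording of follow-up scans in patients without PD at discontinuation, until PD, death or another treatment.
- Section 7, calendar: brain MRI is marked in the 3-monthly long-term follow-up column, with footnote 5 attached. The same column collects "Survival Status, Subsequent Therapy".
- Section 9.2: brain MRI continues until documented disease progression, compartment not named, on a schedule counted in treatment cycles.

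**Analysis.** Sections 12.2.1 and 12.6.1 give no censoring rule for iPFS. Section 12.2.2 gives one, censoring at the last disease evaluation, for PFS in either compartment.

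**The concern.** A patient whose disease progresses outside the brain first is still at risk for iPFS. At that moment protocol therapy stops, other treatment including radiation may begin off study, and no passage clearly requires further brain imaging. Death is still collected for a year. One component of the primary endpoint therefore remains observed and the other depends on local practice.

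Two things are at stake. First, the Kaplan-Meier median, the 6-month rate and the log-rank comparison with 4.0 months depend on how such patients are handled, and the plan does not say. Second, an unstated rule could be settled after the data are seen.

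A related gap sits in the RANO-BM rules. Section 9.2.5 asks for confirmation 3 months after early radiographic progression and back-dates it if confirmed. It does not say how to count a progression whose confirmatory scan is never obtained, for instance after off-study radiation. Section 9.2.4 says new lesions alone may not be progression under immunotherapy, while the table in 9.2.5 lists them as progression, subject to that confirmation.

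A separate, secondary point: section 2.2.2 defines extracranial PFS, but sections 12.2.2 and 12.6.2 define and analyse only either-compartment PFS.

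**Working it through.** **1. The plan's own figures.** Inputs from section 12.3: 60 patients, accrual a = 22 months, further follow-up f = 12 months, medians 4.0 and 5.2 months, one-sided level 0.15, exponential times. With λ = ln 2 / median,

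P(event) = 1 − [e^(−λf) − e^(−λ(a+f))] / (λa).

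- Median 5.2: λ = 0.1333; 1 − (0.2020 − 0.0108)/2.933 = 0.935, so 56.1 events.
- Median 4.0: λ = 0.1733; 1 − (0.1250 − 0.0028)/3.812 = 0.968, so 58.1 events.

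Simulating the one-sample log-rank test, Z = (E − O)/√E, gives 81.0% power at 5.2 months and a 13.6% false-positive rate at 4.0 months. The stated power of about 81% is reproduced. The printed event probability of 0.9707 is obtained at 5.2 months with f = 18, not 12. That is a separate discrepancy and changes nothing here. Either way, the plan assumes that about 93-97% of patients have an observed iPFS event.

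**2. Following one patient through the text.** Suppose extracranial-only progression under RECIST 1.1. Section 6.4 stops therapy. Footnote 11's 9-weekly imaging does not apply, because the reason for stopping was progression. Footnote 5 leaves imaging to the site and provides for recording only in patients without PD at discontinuation. Section 9.2's schedule is tied to cycles that have ended. Survival follow-up continues. A later death is captured; a later brain progression is captured only if a scan happens to be done and entered.

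**3. Size on the reading nearest the text.** Deaths count as events. Other extracranial-first patients are censored at the last brain image, with none assumed after extracranial progression. Three inputs are not in the documents and are assumed:
- the share s of patients with extracranial progression first: 10, 30 or 50%;
- the correlation r between the two progression times (normal copula): 0, 0.3 or 0.6. The s values are set at r = 0; the realised shares are 7/27/50% at r = 0.3 and 3/21/50% at r = 0.6;
- median survival after extracranial progression: 7.1 months, taken as 12.3 − 5.2 from section 1.2. This is a difference of medians, so only a rough guide.

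The intracranial hazard is λ, the extracranial hazard is λs/(1 − s), and post-progression survival follow-up is capped at 12 months.

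| Case | s = 10% | s = 30% | s = 50% |
|---|---|---|---|
| No loss, false-positive / power | 14% / 81% | same | same |
| r = 0, false-positive | 11% | 6% | 3% |
| r = 0, power at 5.2 months | 76% | 59% | 35% |
| r = 0.3, false-positive | 16% | 18% | 15% |
| r = 0.6, false-positive | 16% | 31% | 44% |
| r = 0.6, death tied to iPFS so it cannot come first | not computed | 22% | 26% |

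At r = 0.6 the Kaplan-Meier median is 4.1/4.5/5.1 months when the truth is 4.0. The futility look in section 12.7 takes off only about 2 points there (30.6 to 28.4% at s = 30%; 44.3 to 42.4% at s = 50%).

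Two forces oppose each other. Censoring survivors back at extracranial progression while keeping the deaths discards event-free time and makes iPFS look worse. If patients who progress early outside the brain also tend to progress early inside it, the unseen brain progressions make iPFS look better. At r = 0 the first force wins, at r = 0.3 they roughly cancel, and at r = 0.6 the second wins.

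**The case against.** The text can be read more kindly. Section 9.2 sits among the RANO-BM rules, section 9.2.2 separates CNS from systemic response, the calendar marks brain MRI in long-term follow-up, and section 6.4 keeps discontinued patients in protocol follow-up. This stands as a possible reading, and it is why the point is that the passages are unreconciled. It does not settle the matter: the calendar mark carries the footnote that makes the scan discretionary, and section 9.2 counts in treatment cycles.

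A reader might infer that recording of brain scans is barred after progression. Footnote 5 does not say so. It provides for recording in one group and is silent on the others.

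A reader might also infer severe inflation of the false-positive rate. Censoring at extracranial progression gives 18/40/74% at r = 0.6 for s = 10/30/50%. Keeping survivors at risk to last contact without brain images gives 25/54/79% at r = 0 with a 7.1-month post-progression median. The documents support neither. The first drops deaths that sections 2.2.1 and 12.2.1 count as events; the second is a rule no passage states.

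Finally, the stated objective is estimation, and 60 patients give wide intervals: about 4.0 × e^(±1.96/√58) = 3.1 to 5.2 months for the median, and about ±12 points on a 6-month rate of 35%. Modest bias would sit inside that. This stands for small s and r. It does not excuse leaving the rule for the primary endpoint open.

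**Conclusion.** The concern holds as a conflict between the endpoint and the follow-up rules, together with a missing iPFS censoring rule. It should be fixed. That conclusion rests on the text and does not depend on the simulation.

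The size is illustrative. On the reading nearest the text the effect runs from a conservative, underpowered test (3% false-positive rate and 35% power at s = 50%, r = 0), through about nominal (15-18% at r = 0.3), to anti-conservative (44% at s = 50%, r = 0.6, or 26% if death is tied to iPFS). Neither direction nor size can be stated without s, r and post-progression survival, none of which the documents give. Confidence in the size is therefore limited, and the extreme figures should not set the severity.

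**What to change.** 1. **Follow-up wording.** Reconcile section 6.4, the section 7 calendar, footnotes 5 and 11, and section 9.2 by naming the compartment that progression refers to in each. For the endpoint, follow intracranial status to RANO-BM progression or death regardless of extracranial progression. At minimum, record every standard-of-care brain image and brain-radiotherapy date at the existing 3-monthly contacts, including after new therapy. No scan is added, and when treatment stops is unchanged.
2. **Section 12.2.1.** State that deaths are events and that other patients are censored at the last brain imaging. Prespecify sensitivity analyses for extracranial progression, new therapy or brain radiotherapy before intracranial progression, and for interval or midpoint dating of intracranial progression found after extracranial progression. Report how many patients fall in each group, and state that sparse later imaging leaves some bias.
3. **Sections 9.2.4 and 9.2.5.** Reconcile the new-lesion statements and prespecify how early radiographic progression without a confirmatory scan is counted, with the alternative as a sensitivity analysis. The choice is the sponsor's.
4. **Separately,** add the analysis of extracranial PFS as defined in section 2.2.2, beside either-compartment PFS, in sections 12.2.2 and 12.6.2.

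**Cost and limits.** Wording changes plus modest data capture at contacts that already collect survival and subsequent therapy. In the simulation with death tied to iPFS (s = 30-50%, r = 0-0.6), 3-monthly brain images in all extracranial-first patients give a false-positive rate of 18-25% with scan-date dating and 14-16% with midpoint dating (power 80-82%). Images in only half of them, with midpoint dating, give 8-19% (power 62-82%). If few brain images are done after extracranial progression, some bias remains.

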12.2.2 Definition of Secondary Endpoints

ORR is the proportion of patients whose best response to protocol treatment are either complete response (CR) or partial response (PR) by the investigator using RECIST 1.1. Patients not meeting these criteria, including patients without any post-baseline tumor assessment, will be considered non-responders.

PFS is defined as the time from Day 1 of protocol treatment until the criteria for disease progression (intracranial or extracranial) is met as defined by RECIST 1.1 and RANO-BM, or death from any cause, whichever comes first. Subjects who have not progressed will be right-censored at the date of the last disease evaluation. If progression occurs in either intracranial or extracranial or both compartments, the criteria for progression-free survival will have been met per RANO-BM.

OS is defined as the time from Day 1 of protocol treatment until death from any cause.

CTCAE V5 will be utilized to define the grade and type of toxicities and adverse events.

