12.3 Sample Size and Accrual

The study will enroll 63 eligible patients who receive at least one dose of the study agent.

The sample size of the study is determined by the analysis of iPFS. To detect an improvement of median iPFS = 5.2 months from 4.0 months in historical control (IMpower 133) (HR = 0.77) using a logrank test, 60 treated patients will be required to achieve approximately 81% power at a one-sided significance level of 0.15. Patients are accrued for a period of 22 months. Follow-up continues for 12 months after the last patient is enrolled. The probability that a patient experiences an event during the study is 0.9707. The expected number of events during the study is 58. It is assumed that the survival time is exponentially distributed. The sample size calculation above is conducted in PASS v16.0.2. Assuming a 5% rate of dropout prior to protocol treatment, a total of 63 eligible patients will be treated by at least one doses of the study agent.

The sample size calculation is determined to have adequate power to reject the null hypothesis when the alternative hypothesis is true for the primary endpoint iPFS. Whether it has sufficient power for addressing secondary endpoints or exploratory analysis is not of concern.

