12.6.2 Analysis Plans for Secondary Objectives

ORR and its 95% CI will be estimated.

Median PFS and OS and their 95% CIs will be estimated using Kaplan-Meier approach. KM curves will be used to characterize PFS and OS. Six-month PFS and 12-month OS rates and their 95% CIs will also be estimated. Cox proportional hazard models will evaluate the relationship between PFS or OS with the patients' baseline characteristics, including age at enrollment, gender, race, and ECOG Performance Status and the estimated HRs and their 95% CIs will be provided.

The types and frequencies of toxicities will be summarized by the severities.

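### Survival follow-up ends one year after progression, so OS censoring depends on progression time and observable late deaths are lost; any bias in the late OS curve is small and of uncertain direction

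*Combined protocol and SAP*

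**What the plan says.** The follow-up rule is in Section 7, Study Calendar, footnote 11: "Once disease progression is documented, subjects will be followed for survival every 3 months for 1 year from documented progression". The footnote allows this contact by clinic visit, phone or other means.

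Section 12.2.2 defines the endpoint without a time limit: "OS is defined as the time from Day 1 of protocol treatment until death from any cause". The only censoring rule in that section belongs to PFS: "Subjects who have not progressed will be right-censored at the date of the last disease evaluation". None is given for OS.

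Section 12.6.2 plans these OS analyses:
- "Median PFS and OS and their 95% CIs will be estimated using Kaplan-Meier approach"
- "Six-month PFS and 12-month OS rates and their 95% CIs will also be estimated"
- a Kaplan-Meier curve
- "Cox proportional hazard models will evaluate the relationship between PFS or OS with the patients' baseline characteristics"

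On study length, Section 12.3 says "Patients are accrued for a period of 22 months" and "Follow-up continues for 12 months after the last patient is enrolled", which makes 34 months. The synopsis estimates a study duration of 40 months.

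**The concern.** Kaplan-Meier and Cox analyses assume that patients censored at a given time have the same later risk of death as those still followed. Here the censoring time is set by progression, which is a strong predictor of death. A patient who progresses at month 3 leaves survival follow-up at month 15; one who has not progressed stays under observation. After month 12 the risk set therefore loses progressed patients and keeps unprogressed ones.

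The plan also gives up deaths that it could record by telephone. The rationale (Section 1.4) offers the trial as a description of outcomes in this population and expects no harm to survival from deferring whole brain radiotherapy. The late part of the OS curve bears on that expectation.

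**Working it through.** **1. What follows from the text alone.** Let P be the time of progression and A the potential follow-up from Day 1 to study end. For a progressed patient, OS is censored at min(A, P + 12).
- With 22 months of accrual and 12 months of further follow-up, A runs from 12 to 34 months. In a 40-month study it runs from 18 to 40.
- Because P > 0, nobody is censored by this rule before month 12.
- An early enrollee with A = 34 who progresses at 5.2 months leaves at 17.2 months, which gives up 34 - 17.2 = 16.8 months. A late enrollee with A = 12 loses nothing.

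**2. The plan's own event figure, to see which study length it implies.** For exponential times with λ = ln 2 / 5.2 = 0.1333, uniform accrual a = 22 and further follow-up f, the event probability is 1 - [exp(-λf) - exp(-λ(a+f))] / (λa).
- f = 12: 0.9348, or 56.1 events of 60.
- f = 18: 0.9707, or 58.2 events of 60.

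Section 12.3 states 0.9707 and 58 events. These match 18 months of follow-up (22 + 18 = 40, the synopsis duration) and not the 12 months that the same section gives. Both study lengths are therefore carried below.

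**3. Size.** The documents state no OS assumption for this trial. The check uses an illness-death model with medians from Section 1.2 (PFS 5.2, OS 12.3 months). The assumptions that are not in the documents were varied:
- share of first events that are deaths without progression: 0-30%, base 15%
- Weibull shape of post-progression survival: 0.5-1.5, base 1
- gamma frailty shared by progression and death: variance 0 or 0.5
- long-term non-progressors: none or 12%

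Kaplan-Meier OS with study-end censoring only is compared with OS also censored at P + 12.

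| Base case, per 60 patients | 34 months | 40 months |
|---|---|---|
| Deaths seen, no cap | 46.2 | 52.0 |
| Deaths seen, footnote 11 | 41.2 | 44.4 |
| Deaths lost | 5.0 | 7.6 |
| Patients censored by the rule | 8.8 | 11.2 |
| At risk at 24 months, no cap | 5.0 | 8.0 |
| At risk at 24 months, footnote 11 | 2.8 | 4.5 |

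With the OS median held at 12.3 months, the assumptions give about 6-13 patients censored and 3-6 deaths lost over 34 months, and about 7-16 patients and 4-8 deaths over 40 months.

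**4. Bias in the curve.** In the base case OS reads 32.3% against a true 31.3% at 18 months, 20.4% against 18.2% at 24, and 12.8% against 10.3% at 30. The 24-month error depends on the post-progression hazard:
- Constant or rising: about +1 to +4 points.
- Falling, no shared frailty: -0.1 with shape 0.7 and -2.2 with shape 0.5, reaching about -3 at the extreme.
- Falling (shape 0.7) with shared frailty: +1.7.

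The sampling SD of the 24-month estimate with 60 patients is 6-8 points.

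**5. The pre-specified OS quantities.**
- 12-month rate: unchanged in every scenario.
- Median: in simulated 60-patient trials over 34 months the mean estimate was 12.18-12.21 months without the cap and 12.25-12.27 with it; its SD rose from 1.7-2.1 to 1.8-2.2 months. A true median of 15.0 reads as 15.1.
- Cox: with a binary covariate acting on both progression and post-progression death, the OS hazard ratio was 1.66 without the cap and 1.67 with it, and 2.48 against 2.49 for a stronger effect. The standard error of the log hazard ratio rose from about 0.30 to 0.32.

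**The case against.** The best defence is that the plan names two OS numbers, the median and the 12-month rate, and neither is materially disturbed. No estimate at 18, 24 or 30 months is planned. Administrative censoring already leaves only about 5 of 60 patients at risk at 24 months in a 34-month study, and a 2-point shift there is well inside the sampling error. OS is secondary, Section 12.3 disclaims any concern about power for secondary endpoints, and limiting survival contact is a legitimate choice of resources. All of this stands, and it keeps the point minor.

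It does not remove the point. The full OS curve and the OS Cox models are planned and use the period after month 12. The follow-up sentence in Section 12.3 gives a study-level duration; it does not tell sites to keep contacting a patient beyond the limit in footnote 11.

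A reader might go further and infer that the rule biases late OS upward. The documents do not support that as a general statement, because they give no post-progression hazard and a falling one can remove or reverse the error. A reader might also infer biased Cox hazard ratios; the check found some loss of precision and no material bias.

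**Conclusion.** The point holds as a cheap improvement. Two parts follow from the wording and need no model: OS censoring depends on progression time, and patients leave survival follow-up while the study could still observe them. The number of deaths lost (about 3-6 of 60 over 34 months, 4-8 over 40) rests on the background medians applying to this population and on the assumed range of post-progression hazards. The direction of any error in the late curve is not established. Its size, a few points at 24 months, is smaller than the sampling SD. The primary iPFS analysis and its sample size do not depend on this rule.

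**What to change.** Amend footnote 11 so that all patients are followed for survival every 3 months, by phone or record check, until death, withdrawal of consent, loss to follow-up or end of study, whatever their progression date. This would also cover patients who start a new cancer treatment before progression, for whom the footnote now gives no survival schedule.

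Add to Section 12.2.2 that patients not known to have died are censored for OS at the last date known alive.

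Define end of study once. The 12 months after last enrolment in Section 12.3 and the 40-month duration in the synopsis must be reconciled first, since the stated event probability fits 18 months of follow-up.

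The cost is extra survival contacts for roughly 6-16 patients within the planned duration, with no added visits, scans or change of treatment.
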